5.2 Discontinuation from trial

The subject will be advised in the informed consent form that he/she has the right to discontinue from the trial at any time without prejudice.

Subjects must be discontinued from the trial under the following circumstances:

Clinical trial protocol	Date:	12-Nov-2021	
Trial ID: SU-G-01	Version:	4.0	
EudraCT No. 2020-000455-12	Status:	Final	
CONFIDENTIAL	Page:	31 of 77	

- If, in the investigator's opinion, continuation in the trial would be detrimental to the subject's well-being
- If informed consent is withdrawn

If found required by ALK after discussion with the investigator, subjects may be discontinued from the trial under the following circumstances:

- If subject is treated with prohibited medication as defined in Table 2
- In case of protocol deviation, violation of eligibility criteria or deviation from the treatment plan specified in the protocol (e.g. incorrect administration of the IMP)
- Simultaneous or previous participation (within 30 days of randomisation) in other clinical trials of an approved or non-approved investigational medicinal product

In case a subject discontinues from the trial, the discontinuation page in the electronic case report form (eCRF) should be completed. On the discontinuation page the investigator should record the date of the discontinuation from the trial, the person initiating the discontinuation, and the primary reason for discontinuation. If an adverse event (AE) is involved in a discontinuation, this must be recorded as the primary reason. In all cases, the primary reason for discontinuation must be recorded in the eCRF and in the subject's medical records. A follow-up visit on the subject is necessary to establish trial-related AEs that must be reported in accordance with the appropriate procedures.

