12.1 Definitions

Adverse events

An AE is any untoward medical occurrence in a clinical trial subject, and which does not necessarily have a causal relationship with the administered IMP.

An AE can therefore be any unfavourable and unintended sign (including e.g. an abnormal laboratory finding or medication error), symptom or disease, whether or not considered related to the IMP.

The following events should not be recorded as AEs:

- A pre-planned procedure, e.g. a surgical intervention, unless the condition for which the procedure was planned has worsened since the informed consent form was signed.
- Pre-existing conditions documented as medical history. However, any worsening in severity or frequency of a pre-existing condition during the clinical trial period must be regarded as an AE.

Serious adverse events

An SAE is any untoward medical occurrence or effect that at any dose:

- Results in death
- Is life-threatening (this refers to an event in which the subject was at risk of death at the time of the event; it does not refer to an event that hypothetically might have caused death if it had been more severe)
- Requires in-subject hospitalisation, regardless of duration, or prolongation of existing hospitalisation
- Results in persistent or significant disability or incapacity
- Is a congenital anomaly or birth defect
- Is judged to be medically important (this refers to an event that may not be immediately lifethreatening or result in death or hospitalisation, but may jeopardise the subject or may require intervention to prevent one of the other outcomes listed above)

Events of medication error, overdose and abuse

Medication error, misuse, overdose and abuse of IMP(s) must always be collected in line with adverse event reporting, with or without associated AEs.

- Medication error: Any unintended failure in the medication treatment process that leads to, or has the potential to lead to, harm to the subject.
- Overdose: Any cumulative dose taken in one day that exceeds the dose intended by this protocol, regardless of whether the dose has caused any AEs
- Abuse: Persistent or sporadic, intentional excessive use which is accompanied by harmful physical or psychological effects
- Misuse: Intentional and inappropriate use

Events of special interest (ESI)

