6.1.2 IMP discontinuation

As pointed to previously, reasons for discontinuation of IMP will be categorised into three categories: 1) due to "IMP-related AE" 2) due to "lack of efficacy" and 3) due to "other reasons". As the eCRF defined that trial- and treatment discontinuation reasons are not corresponding to this tripartite split the following mapping form the observed data in the eCRFs to the three categories will be performed:

Treatment discontinuation reasons presented in the eCRF's "Visit Status"-form are:

• Severe or persistent symptoms of eosinophilic oesophagitis

- Pregnancy
- Physician's decision
- Adverse event(s)
- Asthma difficult to control
- Treatment is unblinded

while withdrawal from trial reasons presented in eCRF's "End of study"-form are:

- Screening failure
- Withdrawal of consent
- Adverse event(s)
- Lost to follow-up
- Non-compliance with protocol
- Pregnancy
- Death
- Lack of efficacy
- Randomisation code broken
- Other

Before DBL, the discontinuation of treatment is re-defined and the subject specific list of discontinuations and their classifications to fit the estimand framework is in supplementary document to the SAP: Documentation of Trial Analysis Sets.

Discontinuation due to AEs

A subject is considered discontinued from the treatment due to IMP-related AE if the following conditions are met:

- 1. If, in the "Visit status"-form or End of study"-form reported reason for treatment discontinuation or withdrawal from trial is:
 - Severe or persistent symptoms of eosinophilic oesophagitis
 - Adverse event(s)
 - Asthma difficult to control
- 2. And AEs related to discontinuation are classified as possibly or probably related.

Discontinuation due to lack of efficacy

A subject is considered discontinued from the treatment due to lack of efficacy if the following conditions are fulfilled:

1. If, in the "End of study"-form, it is noted that the subject withdrawal from trial due to "Lack of efficacy".

Discontinuation due to "other reasons"

A subject is considered discontinued from the treatment due to other reasons if the subject discontinues treatment or withdrawal from trial due to other reasons than mentioned above.

Date: 27-Oct-2023 Version: 1.0 Status: Final Page: 21 of 47

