6.2.1 Handling of intercurrent events and missing data for the trial product estimand – main approach

The relevant endpoints will be compared between treatment groups using the trial product estimand with population FAS and data point DPS1. This means that subjects for whom the endpoint is missing (the exclusion of daily diary data due to discontinuation of trial treatment) will still be included in the analysis through multiple imputations under the hypothetical situation where subjects continued to take trial treatment as planned. The missing data imputation is done using the following rules:

• For subjects that discontinue trial treatment due to lack of efficacy, multiple imputation of the missing endpoint will be taken from the placebo group. This assumes that had the subject continued to take trial treatment, they would have experienced similar efficacy to subjects in the placebo arm. Data are assumed to be missing not at random (MNAR).

Statistical analysis plan Trial ID: SU-G-01 EudraCT No.: 2020-000455-12 CONFIDENTIAL	Date: Version: Status: Page:	27-Oct-2023 1.0 Final 22 of 47		
---	---------------------------------------	---	--	--

- For subjects that discontinue trial treatment due to IMP-related AEs, multiple imputation of the missing endpoint will be taken from their own treatment group. This assumes that the level of efficacy that would have been experienced by the subject if they had continued to take trial treatment is unrelated to the occurrence of the AE and, if they had continued to take trial treatment, they would have experienced similar efficacy to subjects in their own treatment group irrespective to randomised treatment. Data is assumed to be missing at random (MAR).
- For subjects that discontinue trial treatment due to any other non-IMP-related reason or subjects that have missing data but completed the trial, multiple imputation of the missing endpoint will be from their own treatment group. This assumes that the level of efficacy that would have been experienced by the subject had they continued to take trial treatment is not related to their discontinuation of trial treatment. Data is assumed to be MAR.

In summary, missing data is imputed based on the following observed on-treatment data (Table 5):

Table 5: Sources of observed data used for imputation under the primary estimand.

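### Recording any involved AE as the primary reason gives active-arm donors, in the primary analysis, to active-arm subjects who withdraw because their grass rhinoconjunctivitis worsened

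*Protocol*

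**What the plan says.** **Recording.** Protocol 5.2 asks for one primary reason when a subject leaves the trial and sets a precedence: "If an adverse event (AE) is involved in a discontinuation, this must be recorded as the primary reason".

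**What counts as an AE.** Under Protocol 12.1 a pre-existing condition documented as medical history is not an AE, but "any worsening in severity or frequency of a pre-existing condition during the clinical trial period must be regarded as an AE". Rhinitis, conjunctivitis and rhinoconjunctivitis are recorded as history under Protocol 11.4. No current passage exempts allergy symptoms. The protocol's version table shows that version 4.0 removed a bullet in 12.1 that had kept efficacy-endpoint events out of AE recording, so the absence looks intended.

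**Classification.** SAP 6.1.2 sorts IMP discontinuations into three classes.
- Lack of efficacy: only where, on the End of study form, "it is noted that the subject withdrawal from trial due to" lack of efficacy. The Visit Status form lists no such reason.
- IMP-related AE: an AE-type reason on either form, with a second condition: "And AEs related to discontinuation are classified as possibly or probably related".
- Other: "if the subject discontinues treatment or withdrawal from trial due to other reasons than mentioned above". An AE judged unrelated falls here.

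The SAP adds that "the subject specific list of discontinuations and their classifications to fit the estimand framework is in supplementary document".

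**Imputation.** SAP 6.2.1 states: "For subjects that discontinue trial treatment due to lack of efficacy, multiple imputation of the missing endpoint will be taken from the placebo group". It also states: "For subjects that discontinue trial treatment due to IMP-related AEs, multiple imputation of the missing endpoint will be taken from their own treatment group". Table 5 treats the class 'other' in the same way as IMP-related AE. SAP 3.1.1.2 gives the reasoning: a lack-of-efficacy leaver would have had no benefit beyond that seen on placebo.

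**The concern.** The primary analysis chooses the donor arm from the classified reason for stopping. That reason comes from a field whose precedence rule suits safety reporting, not imputation. In this trial the two purposes collide, because the disease whose failure to respond defines lack of efficacy can also be reported as an AE when it worsens.

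Take an active-arm subject who withdraws before the 2nd PGPS because hay fever became worse. Worsening is an AE under 12.1, so 5.2 makes AE the primary reason. Lack of efficacy then does not appear on the End of study form, and SAP 6.1.2 cannot assign that class. If the AE is judged related, the class is IMP-related AE; if not, it is other. Both draw active-arm donors. The subject is credited with the benefit that the estimand says such a subject would not have had, and this happens in the analysis that carries the confirmatory test (SAP 4.1).

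SAP 6.1.2 also gives no precedence when the Visit Status form shows an AE and the End of study form shows lack of efficacy.

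**Working it through.** **Inputs** (Protocol 15.2, repeated in SAP 7): planned TCS difference 1.64; SD 5.5; two-sided 5%; 180 evaluable and 220 randomised per arm; per year 4.5% stopping for AEs and 1% for lack of efficacy. Over two seasons I add the annual rates: 2% lack of efficacy, 9% AE.

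**1. Reproduce the plan's power** (normal approximation).
- Observed cases: SE = 5.5 × √(2/180) = 0.580; 1.64/0.580 − 1.96 = 0.87; power 80.8%, against 80% stated.
- With 220 per arm: SE = 5.5 × √(2/220) = 0.524.
- Primary estimand, 2% of active subjects on placebo donors: 1.64 × 0.98 = 1.607; power 86.5%, against 86% stated.
- Secondary estimand, 2% + 9% = 11% on placebo donors: 1.64 × 0.89 = 1.460; power 79.5%, against 80% stated.

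The dilution step is my reconstruction, since the plan prints no formula. It fits the stated figures if all planned lack-of-efficacy leavers receive placebo donors.

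**2. Who is affected.** Only active-arm subjects, because every placebo-arm row of Table 5 uses placebo donors. Only those with no usable on-treatment entry in the period, because one entry is enough for an average (SAP 6.2; subject 2 in 6.2.5). A stop after the 2nd season is disregarded.

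**3. Size within the planned lack-of-efficacy group.** 220 × 0.02 = 4.4 active subjects. Each one moved from placebo to active donors changes the expected imputed value by 1.64. If a share s has an AE involved, the shift is 1.64 × 0.02 × s. The documents do not give s.

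| s (assumed) | Subjects moved | Shift | Expected difference | Nominal power |
|---|---|---|---|---|
| 0% | 0 | 0 | 1.607 | 86.5% |
| 25% | 1.1 | 0.008 | 1.615 | 86.9% |
| 50% | 2.2 | 0.016 | 1.624 | 87.2% |
| 100% | 4.4 | 0.033 | 1.640 | 87.8% |

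The maximum, 0.033, is 2% of 1.64 and about 0.06 of the SE (0.033/0.524).

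**4. If some planned AE stops are worsened rhinoconjunctivitis.** 220 × 0.09 = 19.8 active subjects. For an assumed share q the additional shift is 1.64 × 0.09 × q: 0.015 at 10%, 0.037 at 25%, 0.074 at 50%, and 0.148 at the extreme of 100%. No value of q is in the documents.

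**5. Direction.** The shift is the fraction moved times the difference between donor pools. It favours active if active is better, has expectation zero if there is no effect, and reverses if active is worse.

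**6. Cover from other analyses.**

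| Analysis | AE judged related | AE judged unrelated |
|---|---|---|
| Trial product, main (6.2.1) | active donors | active donors |
| Trial product, sensitivity (6.2.2) | placebo | active donors |
| Treatment policy, main (6.2.3) | placebo | active donors |
| Treatment policy, sensitivity (6.2.4) | placebo | placebo |
| Tipping point (6.2.7.1) | penalised | penalised |

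The calculations use raw TCS means. They ignore the square-root transformation, the asthma strata and any change in variance from imputation.

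**The case against.** A reader might infer that Protocol 5.2 empties the lack-of-efficacy class, so that lack-of-efficacy leavers in general receive active donors. The documents do not support that. The precedence applies only when an AE is involved, and the End of study form offers lack of efficacy as a reason in its own right. Nor is lack of efficacy the same as worsening. Inclusion criterion 5 requires severe symptoms that remain troublesome despite medication, so a subject whose usual hay fever simply fails to improve has lack of efficacy and no AE under 12.1. The sample-size section also plans for a non-empty class.

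A reader might also infer a bias that always favours active. Step 5 shows that it does not: the routing can slightly enlarge a real effect, but in expectation it does not create one.

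Three further defences have weight. The sensitivity and tipping-point analyses bracket the problem; that is largely true, but none is the confirmatory test, and two of them miss an AE judged unrelated. The subject-level list may already repair individual cases; it may, but it was not available for this review, and 6.1.2 states no rule that restores lack of efficacy once an AE has displaced it. Finally, letting any contributing lack of efficacy override every AE would be as blunt as the present rule and would conflict with the MAR assumption for subjects whose stop was driven by an IMP-related AE. That stands, and the fix below is narrower for that reason.

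**Conclusion.** The point holds for a defined group: active-arm subjects whose withdrawal involves worsened grass rhinoconjunctivitis recorded as an AE, with no usable on-treatment entry in the period. For them the recording rule and SAP 6.1.2 together contradict the assumption in SAP 3.1.1.2. The effect is small: at most about 0.033 TCS points within the planned lack-of-efficacy group, assuming that every one of those 4.4 subjects is recoded, has a missing endpoint, and that the true difference is 1.64. Anything larger rests on an unstated share of AE stops. How many such subjects exist cannot be determined from the documents. It is worth correcting because it affects the confirmatory analysis and the correction costs almost nothing.

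**What to change.** Add a rule to SAP 6.1.2, applied blinded in the subject-level classification list before database lock. For imputation, class a discontinuation as lack of efficacy if the leading AE is worsening of grass rhinitis, conjunctivitis or rhinoconjunctivitis, or if the End of study form gives lack of efficacy. The second part also settles disagreement between the two forms. AE precedence in Protocol 5.2 stays for safety reporting.

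Cost: a few lines of text and a blinded pass through AE data already collected. A few more active subjects would receive placebo donors, so the estimate may be slightly less favourable.

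Separate eCRF items for AE involved and lack of efficacy involved would be cleaner, but the last subject's last visit was on 22-Sep-2023 (SAP 3.2.2), before the SAP date of 27-Oct-2023. That is a point for future trials only.

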5.3 Lost to follow-up

A subject will be considered lost to follow-up if he or she repeatedly fails to return for scheduled visits and is unable to be contacted by the site. Reasonable effort should be made to contact any subject who does not return to the site for scheduled visits during the course of the trial in order to complete assessments and retrieve any outstanding data and medication/supplies. Should the subject continue to be unreachable, he/she will be considered lost to follow-up, and the effort taken to contact the subject should be documented in the subject's medical record.

Data obtained until discontinuation will be used for statistical analyses.

5.4 Replacement of subjects

Subjects who discontinue IMP treatment or from the trial will not be replaced.

6 RANDOMISATION AND TREATMENT BLINDING/UNBLINDING

6.1 Subject ID number

All subjects enrolled must be identifiable throughout the trial. Each subject will be allocated a 5digit subject number in combination with a 3-digit site number to create a unique subject id (e.g. 101-50001).

The subject number will be generated when the subjects' data are entered into the eCRF at the screening visit. Only the investigator is able to reconcile the unique subject number with the identity of the data subject.

Clinical trial protocol	Date:	12-Nov-2021	
Trial ID: SU-G-01	Version:	4.0	
EudraCT No. 2020-000455-12	Status:	Final	
CONFIDENTIAL	Page:	32 of 77	

6.2 Randomisation

The randomisation list will be generated by a trial-independent statistician and will not be accessible to trial personnel involved in the conduct of the trial, until the database has been locked. The treatment allocation will be stratified based on pre-existing diagnosis of asthma in order to ensure equal treatment distribution of subjects with or without asthma.

The randomisation codes will only be made available for the trial data manager and statistician when the clinical database has been locked and all protocol deviations have been identified and evaluated.

6.3 Treatment blinding/unblinding

A double-blind setup will be used, the active IMP and their matching placebo will be similar in appearance and taste and will be packaged identically to maintain the treatment blind. The treatment will be blinded to the subject, the investigator/site personnel and sponsor personnel or delegates who are involved in the treatment administration or clinical evaluation of the subject.

The treatment for a particular subject may be unblinded by the investigator in a medical emergency situation if knowledge of the IMP is necessary for the optimal treatment of the subject. If possible, the trial site must contact ALK prior to unblinding the subject's treatment. However, in case of an emergency, unblinding and appropriate treatment should be the very first action by the site. Unblinding may also be done by the Qualified Person Responsible for Pharmacovigilance (QPPV).

The randomisation code breaking will be performed via interactive response technology (IRT) for this trial. The time, date and reason for unblinding as well as the initials of the person breaking the randomisation code must be recorded.

The IRT will notify the Clinical Research Assistant (CRA) and the sponsor's safety department immediately after the randomisation code is broken. The subject must be discontinued from the trial after the randomisation code is broken.

It may also be necessary to unblind an individual subject's treatment by the sponsor/safety department, for the purposes of expedited reporting to the authorities and/or ethics committees (e.g. in case of a suspected unexpected serious adverse reactions (SUSAR)). In that situation, blinding of other sponsor personnel and of the investigator and subject must be maintained during the trial.

6.4 Subject card

All subjects who have signed the informed consent form will be given a subject card by the investigator or qualified designee, identifying them as participants in a clinical trial. The card will contain trial site information (including direct telephone number) to be utilised in the event of an emergency.

7 RESTRICTED AND PROHIBITED CONCOMITANT MEDICATION

Restricted and prohibited concomitant medications are listed in Error! Reference source not found.. For medication that could possibly interfere with the SPT performed at screening please refer to **Table 7**.

CONFIDENTIAL Page: 33 of 77	ID: SU-G-01 raCT No. 2020-000455-12 NFIDENTIAL	Version: 4.0 Status: Final Page: 33 of 77	ALK
-----------------------------	--	---	-----

All concomitant medications must be appropriately documented in the eCRF. The use of any concomitant medication must relate to the documented medical history, prophylaxis or an AE of the subject.

 Table 2
 Restricted concomitant medications

Product	Time window	Reason
An investigational product other than the IMP	≤ 30 days or 5 half-lives of the product (which ever longest) before visit 2 and until end of trial	Possible interaction between IMPs. Interferes with efficacy and safety evaluations
Antihistamine, routine use and preventive use to treat anticipated adverse events (rescue medication antihistamines provided by sponsor are permitted for treatment of acute allergic symptoms, see section 8.2)		
- Oral, intravenous, nasal or ocular	From V4 until 01 Sep 2022 and from V7 until 01 Sep 2023	Interferes with rhinoconjunctivitis efficacy assessments.
Antidepressant medications -Antidepressant medication with antihistaminic effect	≤ 14 days before visit 2 and until end of trial	Interferes with rhinoconjunctivitis efficacy assessments Interferes with safety evaluation
Antipsychotic medications -Antipsychotic medication with antihistaminic effect	≤ 7 days before visit 2 and until end of trial	Interferes with rhinoconjunctivitis efficacy assessments due to antihistaminic effect. Interferes with safety evaluation
Glucocorticosteroids -unless provided by the sponsor (see section 8.2) -does not include inhaled corticosteroids		Interferes with rhinoconjunctivitis efficacy assessment. Interferes with safety evaluation
- topical (nasal or ocular)	From V4 until 01 Sep 2022 and from V7 until 01 Sep 2023	
 with systemic effect:¹⁵ any oral tablets (OCS is allowed in cases of asthma exacerbation) 	60 days before visit 4 and until end of trial	

¹⁵ Treatment with systemic prednisolone with daily doses below 20 mg should not be discontinued.

Estimated equipotent doses (i.v. or p.o.); 20 mg Hydrocortisone = 5 mg Prednisolone = 5 mg Prednisolone = 4 mg Methylprednisolone = 0,75 mg Dexamethasone (Liu et al. 2013)

Clinical trial protocol	Date:	12-Nov-2021	× 1 1/
Trial ID: SU-G-01	Version:	4.0	
EudraCT No. 2020-000455-12	Status:	Final	
CONFIDENTIAL	Page:	34 of 77	

 any parenteral formulations (intravenous, intra-articular or intramuscular) or depot formulations regardless of treatment days and dose 	≤ 90 days from visit 4 and until end of trial	
Systemic immunosuppressive treatment (ATC code L04, L01) *other than glucocorticosteroids	≤ 90 days before visit 2 and until end of trial	Interferes with rhinoconjunctivitis efficacy assessments.
Biologic treatments, including, but not limited to : anti-IgE -, anti-IL5 -, anti-IL5R and anti-IL4R treatment (e.g. omalizumab, mepolizumab, benralizumab, reslizumab and dupilumab)	≤130 days or 5 half-lives of the product (which ever longest) prior to visit 2 and until end of trial	Safety of subject. Interferes with rhinoconjunctivitis efficacy assessments.
Immunotherapy with any other allergen(s)	From screening visit 1 and until end of trial	Interferes with rhinoconjunctivitis efficacy assessments. Interferes with safety evaluation
Inhaled, topical (nasal or ocular) or oral nedocromil or cromolyn sodium	≤ 14 days before visit 4 and until end of trial	Interferes with rhinoconjunctivitis efficacy assessments
Monotherapy of Long-acting B- agonist (LABA) (LABA in combination with ICS is allowed)	From visit 2 and until end of trial	Interferes with safety evaluation
Nasal or ocular decongestants	\leq 3 days before visit 4 until 01 Sep 2022 and \leq 3 days before visit 7 until 01 Sep 2023	Interferes with rhinitis efficacy assessments

Clinical trial protocol	Date:	12-Nov-2021	
Trial ID: SU-G-01	Version:	4.0	
EudraCT No. 2020-000455-12	Status:	Final	
CONFIDENTIAL	Page:	35 of 77	

